Animal and human studies have demonstrated that moderate intensity exercise when compared to exertional exercise or strength training result in shifting of cytokine expression toward anti-inflammation and diminished markers of oxidative stress.^{7,16,24,35,45} The benefit of early exercise in AIS and sICH in decreasing pro-inflammatory factors has been demonstrated in animal models when exercise is introduced between 24 hours and three days in AIS and at three or four days in sICH.^{40,53-55} An exercise intervention that is standardized in frequency with measureable intensity and duration is necessary to explore the effects of an exercise intervention in acutely ill patients with AIS and sICH. We hypothesize that a balancing of the inflammatory response after sICH can occur with the application of moderate exercise in the acute period.

Objectives (include all primary and secondary objectives)

Primary Objective: to determine the effects of twice-daily, lower extremity CE of 20 minutes duration plus usual care, compared to usual care alone, on the trajectories of M1 versus M2 cytokine phenotypes in the serum and cerebrospinal fluid (CSF).

Secondary Objectives:

- (i) To determine the effects of twice-daily, lower extremity CE of 20 minutes duration plus usual care compared to usual care alone and a third retrospective cohort of patients receiving usual care during the COVID-19 pandemic on, the immediate and sustained physical impairment, disability scores and relevant covariates such as delirium and hospital acquired infections at NCCU discharge and 30 days after hemorrhage.
- (ii) To determine the correlation between serum and cerebrospinal fluid cytokines in patients with external CSF drainage as part of their care.
- (iii) To explore the relationship between pre-morbid physical function and quality of life and changes in inflammatory factors among all participants.
- (iv) To determine the effects of twice-daily, lower extremity CE of 20 minutes duration plus usual care alone on hemispatial neglect as measured by the Sunnybrook Neglect Assessment Procedure on day 1 of the study at transfer from the ICU or discharge from the hospital and 30 days after hemorrhage.

2. Background (briefly describe pre-clinical and clinical data, current experience with procedures, drug or device, and any other relevant information to justify the research)

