After enrollment, the Patient-Reported Outcomes Measurement Information System (PROMIS) Global Measure of Health v1.2 questionnaire for (pre-morbid health) will be administered to the patient or their LAR depending on the patient's ability to complete the form. At the last follow-up visit the patient or LAR will complete the Stroke Impact Survey. Additionally, the Sunnybrook Neglect Assessment Procedure will be administered to the patient on day 1 of the study, on transfer from the ICU or discharge from the hospital and at 30 days after the hemorrhage.³¹ If the patient is assessed as not having neglect at the time of enrollment or is found not to have neglect as measured by the assessment procedure then they will not have to complete this measure at subsequent time points.

The intervention group will receive two CE sessions per day after randomization with a unit owned cycle (Reck Motomed Letto, Germany). Sessions will be held at least 2 hours apart to allow for patient rest and activities of patient care. The clinician will set the device to an automatic program where passive cycling will be initiated and the device will provide resistance if the patient attempts to actively cycle. Vital signs (e.g., heart rate, blood pressure, pulse oximetry, intracranial pressure) will be monitored continuously by a study team member present at the bedside during the CE session, if an

Figure 1: Supine cycle ergometer

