Promis Global Measure of Health v1.2 to patient or legally authorized representative (LAR)		X								
Stroke										X

Impact Survey to patient or LOR										
---------------------------------	--	--	--	--	--	--	--	--	--	--

b. Study duration and number of study visits required of research participants.

The study will enroll patients for approximately two years. Each patient will receive study interventions or procedures depending on group assignment for 7 days, assessment of motor function and physical/cognitive functioning on transfer from the NCCU or 1 day after the last study day if the patient completed study activities outside of the NCCU and 30 days (-10 days, +30 days) after occurrence of sICH. We will allow a 30 day time period in which to contact the patient if they are not able to be contacted on the 30th day for a total study period of 60 days. If a patient is seen in clinic prior to the 30 day period after the hemorrhage, follow-up assessments will be performed at that time. The stroke service currently collects a modified Rankin score for all ischemic and hemorrhagic stroke patients at 90 days via phone as a standard of care. We will record this value for all patients in this study. If a patient is not scheduled for an in-person visit after discharge, only the 90 day modified Rankin scale will be collected as an outcome measure.

c. Blinding, including justification for blinding or not blinding the trial, if applicable.

This pilot trial cannot be blinded because of the use of the supine cycle ergometer which is a large piece of equipment introduced into the patients' rooms in the intervention group twice per day during the initial study period, however outcome measures at NCCU transfer and 30 days will be obtained by a study team member blinded to the participant's group assignment.

d. Justification of why participants will not receive routine care or will have current therapy stopped.

Current therapy will not be stopped. Participants will receive the study intervention in addition to usual care.

e. Justification for inclusion of a placebo or non-treatment group.

In order to detect a signal of cytokine modulation with the intervention regimen of supine cycle ergometry, a control group not receiving the intensive intervention regimen is necessary for comparison.

f. Definition of treatment failure or participant removal criteria.

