a. Primary outcome variable.

Pro-inflammatory cytokines: IL-1 β , TNF α , IL-6; Anti-inflammatory/repair factors: IL-10, BDNF

b. Secondary outcome variables will be measured at discharge and 30 days post-intracerebral hemorrhage or acute ischemic stroke.

- Modified Rankin Scale (mRS)
- Barthel Index will be measured at discharge and 30 days
- Medical Research Council Sum Score and dynamometry to measure muscle strength
- Discharge location (e.g., home, nursing facility), although not well studied, is commonly associated with physical function at discharge.
- SF-12
- Vital signs (e.g., heart, rate, blood pressure, respiratory rate)
- Delirium positive days
- Hospital acquired infections (e.g., catheter associated urinary tract infection and central line associated blood stream infection)
- CSF cytokines and repair factors
- Stroke Impact Survey

c. Statistical plan including sample size justification and interim data analysis.

Sample size was calculated for a fully powered trial and 9% of this sample size will be used for this pilot according to Cocks' methodology.¹⁰ An effect size of 0.28 was used, based on a published single group observational study in critically ill patients with a primary outcome of cytokine change.⁴⁷ Detection of an effect size of 0.28 with power of 80% and an α of 0.05 requires a sample size of 400 for a full trial and 9% represents a pilot sample size of 36 participants. Due to the enrollment of two stroke phenotypes, ischemic and hemorrhagic, we will analyze each cohort separately, therefore 40 participants per cohort are required. Accounting for attrition, up to 100 participants may be consented in order to enroll up to 40 participants per cohort. Each cohort will have 20 participants in each of two arms, intervention and control. It is estimated that at least 3-5 patients will be enrolled per month over 18 months.

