Aim 2: To determine the effects of twice-daily, lower extremity CE of 20 minutes duration plus usual care compared to usual care alone and a third retrospective cohort of patients receiving usual care during the COVID-19 pandemic on, the immediate and sustained physical impairment and disability scores at NCCU discharge and 30 days after hemorrhage.

Data from this aim will be analyzed in the same fashion as described above.

Hypothesis: The CE group will demonstrate decreases in 90-day modified Rankin Scale score, increases in the Medical Research Council sum score (muscle strength) and grip strength, less delirium positive days and hospital acquired infections.

d. Early stopping rules.

If a patient meets the following stopping criteria on >2 consecutive sessions the patient will be withdrawn from the study: change in neurological examination, sustained change in intracranial pressure, blood pressure, heart rate, or oxygen saturation that is outside of provider-prescribed range or significant pain exacerbated by mobilization.

6. Risks

a. Medical risks, listing all procedures, their major and minor risks and expected frequency.

The risks of this study are designed to be minimal. Potential risks to the participant include the following: hemodynamic instability, increased intracranial pressure, skin breakdown associated with the supine cycle ergometer, pain, muscle spasm and musculoskeletal injury.

b. Steps taken to minimize the risks.

Patients are continuously monitored on a cardiorespiratory monitor with oxygen saturation, heart rate, intracranial pressure (when applicable) and blood pressure, measured by arterial catheter or non-invasive cuff. Blood pressure, heart rate, oxygen saturation, respiratory rate and intracranial pressure will be measured and recorded continuously using the Medical Informatics, Sickbay software application currently installed in the NCCU and collecting data from all cardiorespiratory monitors. Pain will be measured and documented every 5 minutes visual analog scale or behavioral pain scale in patients unable to report pain level.

The NCCU is staffed 24 hours per day by a dedicated team of Neuro Intensivists, fellows and resident physicians assigned exclusively to the unit who can respond immediately to physiologic changes or adverse events when notified. A chain of command is followed when a primary provider is not available to respond due to other emergent patient care duties.

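### A patient with no in-person visit scheduled after discharge contributes only the 90-day mRS, so the 30-day outcomes in objective (i) and Aim 2 would be compared in a subset defined after randomization

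*Combined protocol and SAP*

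**What the plan says.** Section 3b (study duration and number of visits) sets the follow-up at 30 days, with a window of -10 to +30 days. It then adds the restriction: "If a patient is not scheduled for an in-person visit after discharge, only the 90 day modified Rankin scale will be collected". Just before this, it explains that the stroke service obtains an mRS by phone at 90 days as standard care, and states: "We will record this value for all patients in this study".

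Other parts of the document set the 30-day outcomes without that restriction:

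- Secondary objective (i) places the sustained outcomes "at NCCU discharge and 30 days after hemorrhage".
- Study Statistics, b: "Secondary outcome variables will be measured at discharge and 30 days post-intracerebral hemorrhage or acute ischemic stroke". The list there includes mRS, Barthel Index, MRC sum score with dynamometry, and the Stroke Impact Survey.
- Study Statistics, c, Aim 2 concerns "the immediate and sustained physical impairment and disability scores at NCCU discharge and 30 days after hemorrhage".
- Table 1 schedules mRS, Barthel, MRC sum score, grip strength and the Stroke Impact Survey at 30 days. Only the neglect battery (SNAP) carries a condition, and that condition is neglect at the first assessment.
- Section 4, in the rationale for the pre-morbid mRS criterion, names the mRS as an outcome at discharge and 30 days and says the 0 to 6 scale includes death.

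The Aim 2 hypothesis uses a different time point for disability: "The CE group will demonstrate decreases in 90-day modified Rankin Scale score".

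On who may answer, section 3a says: "At the last follow-up visit the patient or LAR will complete the Stroke Impact Survey". On early attendance, section 3b says: "If a patient is seen in clinic prior to the 30 day period after the hemorrhage, follow-up assessments will be performed at that time".

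**The concern.** Whether a visit is scheduled becomes known only after treatment and discharge. A 30-day comparison limited to patients with a visit is therefore not a comparison of the groups as randomized. If visits go mainly to patients who survive and recover well, the 30-day table describes the better recoverers. If cycling alters who is given a visit, the arms are no longer comparable at that time point. Discharge location is itself a listed outcome, and the protocol links it to physical function.

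The statistics section gives no missing-data method, no rule for deaths at 30 days, and no comparison of patients with and without a visit. The pilot's stated aim is to estimate effect size, so both the comparability and the precision of the 30-day estimates matter.

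**Working it through.** **1. What a patient without a visit contributes after discharge**

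| Measure | 30 days, per Table 1 | Patient with no visit, per section 3b |
|---|---|---|
| mRS | all | none at 30 days; 90 days by phone |
| Barthel Index | all | none |
| MRC sum score, grip | all | none |
| Stroke Impact Survey | all (patient or representative) | none |
| SNAP | those with neglect at first assessment | none |

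The two columns cannot both be followed.

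**2. The plan's own sample size.** Inputs from Study Statistics, c: effect size 0.28, power 80%, α 0.05 (two-sided assumed). n per arm = 2(1.960 + 0.842)²/0.28² = 200.2, rounded up to 201. The total of 402 agrees with the stated 400. Then 0.09 × 400 = 36, set at 40 per cohort, 20 per arm. The allowance of 100 consented for 80 enrolled implies 20% attrition. No share without a visit is given. No figure in the plan is disputed.

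**3. Precision at 30 days, one cohort.** SE(d) ≈ √(2/m) for m observed per arm; half-width = t(0.975, 2m − 2) × SE. The share seen is assumed, because the documents give none.

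| Share seen | m per arm | SE | 95% half-width |
|---|---|---|---|
| 100% | 20 | 0.316 | 0.64 |
| 80% | 16 | 0.354 | 0.72 |
| 70% | 14 | 0.378 | 0.78 |
| 60% | 12 | 0.408 | 0.85 |
| 50% | 10 | 0.447 | 0.94 |

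**4. Can a bias be derived?** Take a normal recovery score with SD 1 and true difference δ. Assume correlation ρ between recovery and the tendency to have a visit, a share s of controls seen, and the same visit rule in both arms. With c = Φ⁻¹(s), the control mean among those seen is ρφ(c)/Φ(c). The cycling mean is δ + ρφ(c + ρδ)/Φ(c + ρδ).

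- For ρ from 0.3 to 0.7 and s of 50% or 70%, the control mean shifts by 0.15 to 0.56 SD toward better recovery.
- A true δ of 0.28 appears as 0.20 to 0.27. Example, ρ = 0.7 and s = 0.5: control 0.558, cycling 0.754, difference 0.196.
- With δ = 0 the expected difference stays 0. With ρ = 0 there is no bias, only lost precision.

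On a binary scale, assume 60% (control) and 45% (cycling) poor outcomes, with 80% seen after a good outcome and 30% after a poor one.

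- Observed poor outcome, control: 0.18/0.50 = 36%. Cycling: 0.135/0.575 = 23.5%.
- The risk difference falls from 15 to 12.5 points, and the risk ratio moves from 0.75 to 0.65.
- The odds ratio is unchanged: (0.45/0.55)/(0.60/0.40) = 0.545 and (0.135/0.44)/(0.18/0.32) = 0.545.

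If visit rates differ by arm, a difference can arise from none. Assume 60% poor in both arms, 80% seen after a good outcome, and 30% (control) against 45% (cycling) seen after a poor one. Observed poor outcome is 0.18/0.50 = 36% against 0.27/0.59 = 46%. Swapping the two rates reverses the sign.

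So the apparent bias depends on the scale and on visit rules that the documents do not state.

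**The case against.** The strongest reply is that the same section protects a longer-term disability measure. The 90-day mRS is taken by phone, is to be recorded for every patient, and is the disability measure named in the Aim 2 hypothesis. A patient dead by day 30 is also dead at day 90, so deaths are captured there. This stands. A reader might infer that the whole sustained-recovery question is answered only in a selected subset; the documents do not support that. However, 90 days is not a time point of objective (i), and the 90-day mRS does not replace Barthel, strength, grip, SNAP or the survey. Section 3c promises a blinded assessor for NCCU transfer and 30 days but does not mention the 90-day call.

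A second reply is that selection by recovery is inferred. This also stands: no section says who is scheduled for a visit. The link between discharge location and function makes such selection plausible but does not establish it. If every patient were given a visit, nothing would be lost. The illustrations above show a mechanism and do not estimate this trial's bias. In the binary example with the same visit rule in both arms, the 2.5-point change is small beside a standard error of about 20 points with some 10 and 11.5 patients observed.

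A reader might also infer that early clinic assessments have no lower limit. The -10 day window appears in the same paragraph and in Table 1, and the early-clinic sentence can be read as explaining it. That wording is ambiguous, not a demonstrated error.

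Finally, these are secondary outcomes of a pilot, and the in-hospital cytokine outcome is unaffected.

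**Conclusion.** The conflict is certain from the text. Section 3b withholds every 30-day measure from a patient with no scheduled visit, while objective (i), Table 1, the section 4 rationale, Study Statistics b and Aim 2 set those outcomes at 30 days without that condition. The 30-day comparison would therefore be made in a subset defined after randomization.

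The loss falls on the 30-day mRS, Barthel Index, Stroke Impact Survey, MRC sum score, grip strength and SNAP; the 90-day mRS is protected. Under-representation of deaths and of the more disabled at 30 days is plausible, but neither its size nor its direction can be derived. The loss of precision follows once a share is assumed: the half-width is 0.72 if 80% are seen and 0.94 if 50% are seen, against 0.64 with complete follow-up. This is a cheap improvement.

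**What to change.** Replace the restricting sentence in section 3b with wording such as: If no in-person visit is scheduled, the blinded team member will obtain the mRS, Barthel Index and Stroke Impact Survey by phone or video from the patient or legally authorized representative, within the 30-day window (-10, +30 days). Patients who have died are scored mRS 6. The mode of assessment and the respondent are recorded.

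In addition:

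- Limit only MRC sum score, grip strength and SNAP to in-person visits, and label their 30-day results as an in-person subset.
- Report visit status by arm, within each stroke cohort.
- State that the early-clinic sentence applies only within the -10 day window.
- Bring Table 1, Study Statistics b and Aim 2 into line with the revised section.

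The cost is protocol wording and one extra call for each patient without a visit, made by the assessor already planned. The downside is that some Barthel scores will come by phone or from a proxy, which is why the mode is recorded. The change does not remove selection from the strength, grip and neglect results. It also does not supply 30-day scores for the retrospective pandemic cohort, whose data come only from the chart.

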- a) A 2 teaspoon sample of the patient's serum on the day of enrollment and two additional times during the seven day study period timed with routine collection of blood, when possible, for daily blood tests while the patient is in the hospital. Blood samples will be collected from an existing arterial or central line or via venipuncture. The initial blood sample will be collected on study day 1 prior to cycling in the intervention group and between 8 am-12 pm in the control group. Subsequent samples will be drawn after the second cycling session and between 2 pm and 6 pm in the control group.
- b) A 4-5 mL sample of saliva on the day of enrollment and two additional times during the seven day study period. Saliva will be collected between 8 am-10 am in all participants and prior to the first cycling session of the day for the intervention group.
- c) A 4 mL sample of cerebrospinal fluid (CSF) on the day of enrollment and two additional times during the seven day study period timed with collection of other sampling, when an external ventricular drain is in place as a part of care. CSF sampling will occur in patients with an external ventricular drain inserted as part of their care and will end after 3 samples or when the drain is discontinued. Efforts will be made to time CSF sampling with planned sampling, if possible and sampling will be performed by a nurse or physician study team member trained in the skill as part of their job using aseptic technique. The initial CSF sample will be collected on study day 1 prior to cycling in the intervention group and between 8 am-12 pm in the control group. Subsequent samples will be drawn after the second cycling session and between 2 pm and 6 pm in the control group.

All samples will be placed on dry ice, centrifuged and stored in a -70 degree Celsius freezer within 1 hour of obtaining the sample. Samples will be labeled with de-identified data (patient study number and date only).

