If a patient meets the following stopping criteria on >2 consecutive sessions the patient will be withdrawn from the study: change in neurological examination, sustained change in intracranial pressure, blood pressure, heart rate, or oxygen saturation that is outside of provider-prescribed range, significant pain exacerbated by mobilization.^{22,34}

g. Description of what happens to participants receiving therapy when study ends or if a participant's participation in the study ends prematurely.

Upon study procedure completion participants will continue to receive usual care.

4. Inclusion/Exclusion Criteria

Inclusion criteria:	Rationale:
Age \geq 18 years	Spontaneous intracerebral hemorrhage and acute ischemic stroke is typically a disease of the adult.
Supratentorial intracerebral hemorrhage with or without intraventricular hemorrhage	Only patients with a supratentorial ICH will be included due to the fact that patients with infratentorial ICH often require surgery, introducing an overlay of inflammation above that which is caused by the ICH itself. It is known that intraventricular hemorrhage increases severity of illness and mortality, however it is a common co-occurring process in patients with ICH and should be studied concurrently. ¹³
Acute ischemic stroke with a Medical Research Council Sum Score (MRCSS) of <27.	Patients with a clinical diagnosis of stroke and motor weakness as identified by the MRCSS as less than 27. ²¹
Pre-morbid modified Rankin Score of 0-2	The modified Rankin Score (mRS) is a commonly

	used tool to quantify disability after stroke and is scored from 0 to 6 with higher scores describing increased disability including death. The mRS will be used to characterize a patient's pre-morbid functional status correlating with a patient's potential for recovery after stroke as well as an outcome measure at discharge and 30 days after hemorrhage. ^{5,13} Patients with a mRS >2 prior to admission have poor potential for recovery.
Patient must be able to provide informed consent or have a legally authorized representative to provide consent on their behalf	
Exclusion criteria:	

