Descriptive statistics will be used to report sociodemographic variables. Baseline characteristics will be compared between the two groups. If they are found to be similar, post-intervention outcomes will be compared between the groups. If the baseline characteristics are found to be different, an adjusted analysis as described below will be conducted. Mean (SD) or median (IQR) will be used to describe continuous variables, and frequency (%) will be used for categorical variables. Mean differences in cytokines between the three time points (baseline, day 3 and day 7) will be calculated for each participant in the intervention and control groups. We will also plot data over time by group. Assumptions of normality will be checked and appropriate parametric or non-parametric tests will be used to detect absolute mean differences due to the small sample size, with an a priori significance level of 0.05, although the primary aim of this study is to estimate effect size. Data quality will be ensured by analyzing all samples in duplicate and procurement of samples will be performed by the same investigator. Statistical analysis will be performed using Stata 14.0 (College Station, Texas).

Primary aim (1): To determine whether a regimen of twice daily 20-minute sessions of CE plus usual care administered to patients with sICH and AIS (n=20) increases cytokines of the M2 phenotype and decreases cytokines of the M1 phenotype within 10 days of sICH when compared to a similar group of patients with sICH receiving usual care only (n=20).

The effect size, absolute difference between the two groups and the standard error of the difference will be estimated. The standardized difference will be estimated using Cohen's d. A two-sample t-test will be used to detect differences between post-test outcomes. If the baseline outcome is different, an analysis of covariance (ANCOVA) will be used to compare the outcomes between the two groups adjusting for the baseline difference as a covariate.

Hypothesis: Patients in the CE group will demonstrate an increase in cytokines of the M2 phenotype and a decrease in the M1 phenotype when compared to the group receiving usual care only.

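### The session-stopping rule withdraws patients from the study, not only from cycling. On the likeliest reading this loses primary-outcome data in the cycling arm alone, rarely and with small expected bias, and a few sentences would repair it.

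*Combined protocol and SAP*

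**What the plan says.** Section 3f (participant removal criteria) states: "If a patient meets the following stopping criteria on >2 consecutive sessions the patient will be withdrawn from the study". The criteria are neurological change, sustained change in intracranial pressure or in vital signs beyond the range the provider has set, and significant pain. Early stopping rules, under Study Statistics, has the same consequence: "on >2 consecutive sessions the patient will be withdrawn from the study: change in neurological examination". Neither place limits the withdrawal to cycling.

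Section 3a describes study sessions for one arm: "The intervention group will receive two CE sessions per day after randomization". For blood and CSF it sets the post-baseline draw time by arm: "Subsequent samples will be drawn after the second cycling session and between 2 pm and 6 pm in the control group". Saliva has one window for everyone: "Saliva will be collected between 8 am-10 am in all participants". Table 1 places the samples on study days 1, 3 and 7.

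Section 3g, whose heading asks what happens when participation ends early, says only: "Upon study procedure completion participants will continue to receive usual care". Section 3b adds, of the routine 90-day modified Rankin score: "We will record this value for all patients in this study". The statistical plan compares post-test cytokines between arms and describes its tests as secondary in purpose: "although the primary aim of this study is to estimate effect size". It names no analysis set and no handling of withdrawn patients.

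**The concern.** A patient who tolerates cycling badly leaves the study. A control patient with the same neurological or physiological change stays in and is sampled. Loss that depends on assigned arm and on clinical course can distort a randomised comparison.

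The criteria mostly mark instability, and the Abstract says that the pro-inflammatory phenotype is thought to worsen secondary brain injury. If the patients removed have higher pro-inflammatory markers, the cycling arm looks better on those markers than it should. The direction for IL-10 and BDNF cannot be told from the plan. With 20 per arm in each cohort, one patient is 5% of an arm.

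The sampling text adds a practical gap. Even a team that wished to keep sampling a patient who had stopped cycling would have no stated draw time for blood or CSF, because the cycling arm's time is tied to a session.

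**Working it through.** The plan gives no figure for these withdrawals, so there is none to reproduce. As a yardstick, its planning effect of 0.28 does reproduce its full-trial size: 2(1.960 + 0.842)²/0.28² is just over 200, so 201 per arm and 402 in total, against the stated 400. Nothing below bears on that number.

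**Inputs from the plan.** 7 days × 2 sessions = 14 sessions per patient; more than 2 consecutive means a run of at least 3; 20 cycling patients per cohort, 40 in all (Study Statistics, c); 0.6-2% of sessions terminated in cited trials (Background); 1 adverse event in 541 sessions, or 0.18% (Risks, b).

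**Assumed.** Within-patient correlation of stops (ICC), and correlation between severity and the marker.

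**Timing.** Sessions 1-2 fall on study day 1, 3-4 on day 2 and 5-6 on day 3. The earliest third stop is session 3, on day 2. The day-3 blood follows session 6, so a third stop by session 5 loses both post-baseline samples.

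**Frequency, independent sessions.** With stop probability p, P(run of 3 in 14) ≈ p³[1 + 11(1 − p)].
- p = 0.006: 2.16×10⁻⁷ × 11.934 = 2.6×10⁻⁶
- p = 0.02: 8×10⁻⁶ × 11.78 = 9.4×10⁻⁵

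An exact Markov chain gives the same values.

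**Frequency, clustered sessions.** Let each patient's stop rate be beta-distributed with mean μ, a = μ(1/ICC − 1) and b = (1 − μ)(1/ICC − 1). Then P = Σ c_k B(a + k, b + 14 − k)/B(a, b), where c_k counts 14-session sequences with k stops that contain three in a row. The last column is 1 − (1 − P)⁴⁰.

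| Session rate | ICC | P per patient | Expected per 20 | At least one of 40 |
|---|---|---|---|---|
| 0.6% | 0 | 0.0000026 | 0.00005 | 0.01% |
| 2% | 0 | 0.000094 | 0.0019 | 0.38% |
| 0.6% | 0.05 | 0.00035 | 0.007 | 1.4% |
| 2% | 0.1 | 0.0040 | 0.081 | 14.9% |
| 0.6% | 0.3 | 0.0039 | 0.079 | 14.6% |
| 2% | 0.5 | 0.0186 | 0.372 | 52.8% |
| 1/541 | 0.5 | 0.0017 | 0.034 | 6.6% |

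At ICC 0.3-0.5, 40-55% of these withdrawals come by session 5.

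**A harsher clustering model.** Suppose the chance of a stop is 0.6-2% after a tolerated session, but an assumed 30%, 50% or 80% after a stopped one. Expected withdrawals per 20 are then 0.13-0.42, 0.36-1.15 and 0.9-2.8. This model also raises the overall stop rate: at 2% and 80% the long-run rate is 0.02/(0.02 + 0.20) = 9%, far above the cited range.

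**Bias if it happens, with no true effect.** For n = 20 the expected largest and second-largest standard normal values are 1.867 and 1.408. If the most severe patients leave and severity correlates ρ with the marker:
- one lost: ρ × 1.867/19 = 0.029 to 0.069 SD for ρ = 0.3 to 0.7
- two lost: ρ × 3.275/18 = 0.055 to 0.127 SD

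The standard error is √(1/20 + 1/19) = 0.320 with one lost and √(1/20 + 1/18) = 0.325 with two.

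**Expected bias.** Multiplying expected withdrawals by the one-patient bias gives 0.079 × 0.029 = 0.002 SD to 0.372 × 0.069 = 0.026 SD at ICC 0.3-0.5, under a tenth of the standard error. At ICC 0.05-0.1 it is 0.007 × 0.029 = 0.0002 to 0.081 × 0.069 = 0.006 SD.

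**The case against.** The strongest reply is that the numbers do not justify concern. The larger frequencies rest on an ICC that the plan does not give, and an ICC of 0.5 means roughly an even chance of stopping again after one stop. The plan's own evidence points to rarity:
- none of the events behind the 0.6-2% rate needed further intervention once cycling stopped;
- the one event in 541 sessions was a dislodged arterial line, which is not a withdrawal criterion;
- the unit's own data show no clinically significant changes in 39 sessions, and nothing that ended a session in 32.

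All of this stands, and it is why the point is minor. Two limits apply. The internal sets average 39/39 = 1.0 and 32/23 = 1.4 sessions per patient, so they say little about runs of three. The trial's criteria also include pain and out-of-range vital signs, so they are broader than the events counted.

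A second reply is that the rule speaks of a patient, not a cycling patient, and the strength-testing text in Section 3a mentions a first session for controls. That mention looks like a drafting slip, because no control session is described anywhere. One-sidedness is therefore a firm inference, not a stated fact.

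Third, the plan consents up to 100 patients to allow for attrition. That protects numbers but does not address selective loss. Fourth, research sampling in a patient who has just had a neurological change is a burden. That is right, and the fix makes it subject to the treating team's judgement.

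A reader might infer that the rule materially biases the cytokine result, or that it discards every outcome. The documents support neither. No passage links the triggers to cytokine levels, and the 90-day modified Rankin score may still be recorded for these patients.

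**Conclusion.** The point holds as a minor one. The plan twice states a rule that removes patients from the study, probably from the cycling arm only. It can act before either post-baseline cytokine sample, and nothing keeps those patients in sampling.

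The event is probably rare. At the cited rates, the chance of at least one among 40 is at most 0.4% under independence, about 1-15% at ICC 0.05-0.1 and 15-53% at ICC 0.3-0.5. At 1/541 it is at most about 7%, even at ICC 0.5. Neither clustering model is a bound, since its key input is assumed. Expected bias is well below the standard error.

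That the patients lost would be less stable, and would differ in cytokines, is an inference. The case for change is that the loss is one-sided, avoidable and cheap to prevent in a pilot meant to estimate an effect size. It does not rest on a large expected error, and it implies nothing about the size or power of a full trial or about the clinical merit of the stopping criteria.

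**What to change.** Leave the stopping criteria and the decision to stop cycling as they are.

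1. In Sections 3f and 3g and in Early stopping rules, state that withdrawal under this rule ends study cycling and not data collection. The samples and assessments already in Table 1, and the 90-day modified Rankin score, continue unless consent is withdrawn or the treating team judges a research procedure inappropriate.
2. In Section 3a, sample items a and c, state that cycling-arm patients who are no longer cycling have post-baseline blood and CSF drawn in the window already given for controls, 2 pm to 6 pm. Saliva needs no change.
3. In the statistical plan, state that these patients are analysed in the arm to which they were randomised, and report discontinuations and missing samples by arm and reason.

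The cost is a few sentences; no visit or sample is added to the schedule. There are three downsides. The estimate reflects the assigned regimen and may be slightly diluted. Later samples from these patients no longer follow a session. Research sampling continues in patients who stopped cycling.
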